## PRÉCIS

### Background:

- Primary diffuse large B-cell lymphoma of the CNS (PCNSL) and aggressive B-cell lymphomas with secondary CNS involvement (SCNSL) have a poor prognosis
- Most CNS lymphomas (CNSL) exhibit molecular biology features of activated B cell diffuse large B-cell lymphoma (ABC DLBCL)
- We developed VIPOR (venetoclax, ibrutinib, prednisone, obinutuzumab, and lenalidomide [Revlimid®]) treatment in systemic lymphomas as a platform most effective for ABC DLBCL
- All agents in the VIPOR combination achieve meaningful CNS penetration and clinical activity for lymphomas involving the CNS

### Objective:

- To determine the safety and tolerability of VIPOR in participants with PCNSL and SCNSL

### Eligibility:

- Primary diffuse large B-cell lymphoma of the CNS (PCNSL) or non-germinal center B-cell (non-GCB) diffuse large B-cell lymphoma with secondary involvement of the CNS (SCNSL)
- Relapsed/refractory after prior therapy or ineligible for standard frontline therapy
- Age  $\geq 18$  years
- No pregnant individuals
- Adequate organ function

### Study Design:

- A safety study of 10 evaluable participants with PCNSL or SCNSL treated with VIPOR (the original study protocol enrolled 4 participants to Cohort 1, Arm 1 consisting of VIPOR plus nivolumab which is now closed).
- Participants will receive VIPOR in 21-day cycles for a maximum of 6 cycles to collect data on safety and efficacy.
- Accrual ceiling will be set at 16 participants to allow for a few inevaluable participants or screen failures.

## **STATEMENT OF COMPLIANCE**

The trial will be carried out in accordance with International Council for Harmonisation Good Clinical Practice (ICH GCP) and the following:

- United States (US) Code of Federal Regulations (CFR) applicable to clinical studies (45 CFR Part 46, 21 CFR Part 50, 21 CFR Part 56, 21 CFR Part 312, and/or 21 CFR Part 812)

National Institutes of Health (NIH)-funded investigators and clinical trial site staff who are responsible for the conduct, management, or oversight of NIH-funded clinical trials have completed Human Subjects Protection and ICH GCP Training.

The protocol, informed consent form(s), recruitment materials, and all participant materials will be submitted to the Institutional Review Board (IRB) for review and approval. Approval of both the protocol and the consent form must be obtained before any participant is enrolled. Any amendment to the protocol will require review and approval by the IRB before the changes are implemented to the study. In addition, all changes to the consent form will be IRB-approved; an IRB determination will be made regarding whether a new consent needs to be obtained from participants who provided consent, using a previously approved consent form.

## 1 INTRODUCTION

### 1.1 STUDY OBJECTIVES

#### 1.1.1 Primary Objective

- To determine the safety and tolerability of VIPOR in primary DLBCL of the CNS (PCNSL) and secondary CNS lymphoma (SCNSL)

#### 1.1.2 Secondary Objectives

- To determine the overall response rate (CR + PR) of up to 6 cycles of VIPOR in CNSL
- To determine the complete response (CR) rate of up to 6 cycles of VIPOR in CNSL
- To determine the duration of response (DOR) after VIPOR in CNSL
- To estimate the 10-year progression-free survival (PFS) after VIPOR in CNSL
- To assess 10-year overall survival (OS) after VIPOR in CNSL

#### 1.1.3 Exploratory Objectives

- To perform comprehensive molecular profiling of CNSL tumors and explore correlations with clinical response
- To genotype circulating-tumor DNA (ctDNA) from plasma and cerebrospinal fluid (CSF) and correlate to tissue genotyping
- To assess the pharmacokinetics (PK) of venetoclax and ibrutinib in the plasma and CSF
- To study cytokine changes across VIPOR therapy

## 1.2 BACKGROUND AND RATIONALE

### 1.2.1 Primary CNS Lymphoma

Primary diffuse large B-cell lymphoma of the CNS is a rare disease representing less than 3% of all non-Hodgkin lymphoma. It refers to lymphomas that arise exclusively within the brain parenchyma, spinal cord, eyes, cranial nerves, and meninges without systemic involvement.[\[1\]](#) Epidemiological studies show an increased incidence of PCNSL over recent years particularly in those with advanced ages.[\[2\]](#) PCNSL occurs in both human immunodeficiency virus (HIV) negative and positive participants, but HIV-associated PCNSL is virtually always associated with Epstein Barr Virus (EBV) and is biologically distinct from EBV-negative PCNSL.

### 1.2.2 Treatment of Primary Diffuse Large B-cell Lymphoma (DLBCL) of the CNS

Compared to participants with systemic DLBCL, the outcome for subjects with PCNSL is worse. Treatment of PCNSL differs significantly from systemic DLBCL because many chemotherapy agents do not adequately penetrate the blood-brain barrier. Historically, whole brain radiation (WBRT) has been a mainstay of treatment because it is effective, and side stepped the limitations of chemotherapy in penetrating the CNS. However, when used alone, responses are typically short-lived and virtually all subjects relapse.[\[3\]](#) The development of the chemotherapy-based treatments relied heavily on strategies used for solid brain tumors and was not optimized for the treatment of DLBCL. High dose methotrexate (HD-MTX), an agent with good CNS penetration, has been the centerpiece of PCNSL treatment for years; however, when used alone it produces a progression-

free survival of only 7 months. When HD-MTX was followed by whole brain radiotherapy, it produced a high complete remission rate, but no evidence of cure. Further, combined modality treatment that includes WBRT is associated with severe long-term neurotoxicity. For this reason, there has been much interest in developing regimens that obviate the need for radiation. Most promising in this regard are combinations of high dose methotrexate with systemic agents that cross the blood brain barrier, such as cytarabine and ifosfamide, particularly in subjects under 60 years of age. The Bonn group and others have adopted such an approach and have reported promising results with chemotherapy and deferred radiation in younger subjects. In their trial, 9% died of treatment related toxicity. Overall, the median time to treatment failure was 21 months with a median follow-up of 26 months; for those over 60 years of age, the time to treatment failure (TTF) was 15 months and for those under 60 years old, 60% were free from progression at 4 years. These results show that current strategies have a poor outcome with an unacceptably high treatment related mortality, and low rates of cure. Thus, there is an important need to develop more effective and less toxic strategies based on the molecular biology of PCNSL. We have developed a novel chemotherapy regimen for subjects with relapsed and refractory PCNSL that combines ibrutinib with temozolomide, etoposide, liposomal doxorubicin, dexamethasone, and rituximab (TEDDI-R). Although this regimen is highly effective for subjects with relapsed and refractory PCNSL, it can be associated with hematologic toxicities and may not be tolerated by all subjects. Further, some subjects relapse after TEDDI-R, and effective salvage therapies are needed.

### 1.2.3 Molecular Biology of Primary Diffuse Large B-cell Lymphoma of the CNS

PCNSL has a high load of somatic mutations. Approximately, 30-40% have mutations of BCL6. In addition, aberrant hypermutation in the following proto-oncogenes and tumor suppressor genes are found: PIM1 (50%), c-MYC (60%), TTF (70%), PAX5 (60%), and Fas (CD95) (20%). Interestingly, PCNSL almost never leaves the CNS and though many theories have been hypothesized, the reason for this neuro-tropism is not well understood. Theories that may explain this phenomenon include the following: 1) the brain is an immune sanctuary and the malignant B-cells are eliminated in the periphery by a specific antitumor immune response; 2) the malignant B-cells are dependent on a chemokine that is present in high concentrations within the brain such as BCA-1 – B-cell attracting chemokine encoded by CXCL13; 3) the malignant B-cells are dependent on specific adhesion signals; 4) the malignant B-cells are dependent on an antigen that is only found in the CNS.

Accessing tissue to better understand the biology of PCNSL has been very challenging due to the rarity of the disease and the technical challenges of obtaining tissue from the CNS. In addition, interpretation and analysis of CNS tissue have been impeded by the architecture of the CNS – characteristically there is variable cell density, neovascularization, and many infiltrating immune cells. However, four molecular profiling studies have been performed and they all revealed different messages about the biology of PCNSL. In the first of these, Rubenstein et al. looked at 23 cases of PCNSL and contrasted PCNSL with systemic DLBCL. They showed that the oncogenes PIM1 and MYC were highly expressed in PCNSL relative to systemic DLBCL and there was also evidence of high expression of IL4 genes. They also demonstrated high expression of STAT 6 – which is important in interleukin-4 (IL4) signaling - and high levels of this were associated with poor survival, albeit in a small series. In the second of these studies, Tun et al., evaluated 13 cases of PCNSL. They described a characteristic signature that was composed of

extracellular matrix and adhesion-related genes. A third study, by Montesinos-Rongen et al. looked at 21 cases and demonstrated a signature of a late germinal center B-cell and finally Booman et al looked at 9 cases and described a signature that was enriched in genes that were involved in apoptosis and the immune response.[16]

Most PCNSLs that arise in immunocompetent hosts originate from an activated B-cell (ABC) based on molecular biology analyses. In a limited series, PCNSL was shown to have deregulation of the NF-kappa B pathway, which is a defining molecular feature of ABC DLBCL.[17] Other studies have found coiled mutations of the signaling cascade protein – CARD11 – in 16% of PCNSL, activating L265 mutations of MYD88 in 36% of PCNSL, and mutations of CD79B ([name] personal communication), all mutations that are almost exclusively found in ABC DLBCL.[17, 18]

#### 1.2.4 Secondary CNS lymphoma

Secondary involvement of the CNS is an infrequent but often fatal complication of diffuse large B-cell lymphomas (DLBCL) and other aggressive B-cell lymphomas[19]. The term secondary CNS lymphoma (SCNSL) needs to be distinguished from PCNSL. SCNSL involves the brain, eyes, or CSF but either has concurrent systemic involvement of non-Hodgkin lymphoma (NHL) or has relapsed in the CNS after treatment for systemic NHL (isolated CNS relapse). Involvement of the CNS at the time of diagnosis for DLBCL occurs in ~5% of subjects and usually presents as leptomeningeal disease with involvement of the CSF[20]. Risk factors for the development of SCNSL after therapy have been identified and include a high International Prognostic Index (IPI), age > 60 years, elevated serum lactate dehydrogenase (LDH), advanced disease stage, ECOG performance status > 1, extensive extranodal involvement, and involvement of specific extranodal sites (kidney, testes and possibly uterus or breast).[21] A specific clinical predictor algorithm known as the CNS-IPI has been developed and validated based on these risk factors to identify subjects at greater risk of SCNSL after therapy for DLBCL. In a landmark retrospective study, subjects with all 6 of the risk factors (N=13) included in the CNS-IPI had a 32.5% risk of developing SCNSL, while those without any risk factor (N=235) had a 0.0% risk. The CNS-IPI tool is used in routine practice to identify subjects with newly diagnosed DLBCL who should be treated with CNS prophylaxis to prevent late recurrences in the CNS. Furthermore, the occult leptomeningeal disease can be detected by flow cytometry and identifies subjects with low volume involvement who should receive active treatment. However, CNS prophylaxis and/or active initial treatment of CNS disease does not eliminate the risk of developing SCNSL at a later time, as either a component of the systemic relapse or an isolated CNS relapse.

Compared to subjects with systemic DLBCL, the outcome for subjects with SCNSL is worse. The treatment of SCNSL differs significantly from systemic DLBCL because many chemotherapy agents do not adequately penetrate the blood-brain barrier and have been modeled on studies from PCNSL. In a large, international study of 291 subjects with SCNSL, the majority of subjects (87%) developed SCNSL as part of their first relapse, and 39% had a concurrent systemic relapse.[20] These subjects often developed debilitating symptoms and the post-relapse survival was only 3.9 months for the entire cohort. On multivariable analysis of the subjects who were deemed eligible for second-line therapy with curative intent (59% of cohort), subjects aged < 60, with an ECOG PS 0-1, and without parenchymal involvement had a 2-year OS of 62% (95% confidence interval (CI) 36-80). Overall, however, there are few effective treatments for most subjects and SCNSL, and this complication represents a major unmet clinical need. Prospective phase II and III studies

have established the role of high-dose antimetabolites and consolidative therapy, including WBRT or with autologous stem cell transplantation (ASCT), in subjects with PCNSL, but similar data in SCNSL is lacking with only a few small phase II studies suggesting a role for autologous transplantation.[\[22, 23\]](#) Indeed, this strategy is limited in population-based settings due to limited generalizability to most subjects, failure of salvage treatment, toxicity and unsuccessful stem cell harvest.

The molecular biology that confers CNS tropism for aggressive B-cell lymphomas is largely understudied, but recent studies have suggested that certain subsets of DLBCL have a greater risk of CNS spread, and that these tumors may be reliant on chronic active B-cell receptor signaling. Subjects with DLBCL who express both MYC and BCL2 by immunohistochemistry (i.e. ‘dual expressors’) have a greater risk of CNS relapse than a patient without (9.4% vs. 2.4% p=0.001)[\[24\]](#). Although “dual expressor” DLBCL is not a specific biologic entity recognized by the World Health Organization (WHO) Classification of Lymphoid Malignancies, these subjects most commonly are ABC DLBCL. Subjects with ABC DLBCL are most commonly associated with chronic active BCR signaling and the likeliest to respond to inhibitors of Bruton tyrosine kinase (BTK) such as ibrutinib and acalabrutinib.[\[25, 26\]](#) Additional evidence of the underlying biology of SCNSL tumors comes from a recent paper from the [name] lab who studied 574 DLBCL biopsies and comprehensively analyzed them using exome and transcriptome sequencing, DNA copy-number analyses and targeted amplicon resequencing. In this study, they identified four prominent genetic subtypes of DLBCL based on the underlying genetic aberrations.[\[27\]](#) One genetic subtype was termed MCD based on this striking co-occurrence of both *MYD88*L265P mutations and *CD79B* mutations. Importantly, these mutations frequently co-occur in PCNSL, and the MCD subtype was associated with extensive extranodal involvement and had additional acquired mutations that are recurrently mutated in primary extranodal lymphomas. These observations suggest a biologic link between nodal MCD and extranodal lymphomas, including PCNSL. A recent study of SCNSL tumors confirmed that most cases of DLBCL that secondarily involve the CNS are of the MCD genetic subtype.[\[28\]](#)

### 1.2.5 Scientific Rationale and Clinical Activity of VIPOR in systemic ABC DLBCL

Insights into the molecular pathogenesis of lymphoid tumors have identified abnormalities in key survival pathways. Regulation of apoptosis by BCL-2 family proteins is a central regulator of normal B and T cells and lymphoid tumors have acquired multiple mechanisms of deregulation including translocation, amplification, and elevated gene expression from loss of endogenous MiRs that repress BCL-2 expression and gene hypomethylation. More recently, pathogenic B-cell receptor signaling has been identified in B-cell lymphomas and targeting BTK has shown clinical activity across B-cell lymphomas. In particular, mutations affecting the BCR receptor and downstream signaling molecules have been identified in ABC DLBCL where they lead to enhanced NF $\kappa$ B activation. Lenalidomide inhibits NF $\kappa$ B through its effect on IRF4. Furthermore, lenalidomide affects expression of multiple other proteins through its effect on cereblon E3 ubiquitin ligase and has immune-modulatory properties.

In the development of venetoclax, ibrutinib, prednisone, obinutuzumab, and lenalidomide (Revlimid), we hypothesized that inhibiting multiple pathogenic survival pathways would leverage the efficacy of targeted agents in systemic lymphomas. To help address this hypothesis, we first assessed if combinations of these agents were synergistic in vitro and in murine tumor models and showed synergy between BTK and BCL-2 inhibitors and lenalidomide. Further, in vitro studies

indicated that venetoclax inhibits the development of ibrutinib resistance in ABC DLBCL (unpublished data from the [name] lab).

A major limiting factor for targeted therapy in lymphomas is the need for continuous dosing, which precludes the ability to give multiple agents. Hence, we developed VIPOR (NCT03223610) in relapsed/refractory B-cell lymphomas with a fixed-duration schedule [29]. The regimen was found to be safe with no unexpected toxicities and no maximum tolerated dose identified. The main toxicities are hematologic with grade 3/4 neutropenia, thrombocytopenia, and anemia occurring in 50%, 38%, and 15% of subjects and 27%, 16%, and 3% of cycles, respectively. Importantly, this study excluded subjects with CNS involvement.

#### 1.2.6 Scientific Rationale for VIPOR in CNS lymphomas

The CNS penetrance and pharmacokinetics of the individual components of VIPOR have been evaluated in several clinical trials. A phase 1 study (NCT01542918) of lenalidomide with or without intraventricular rituximab for relapsed/refractory CNSL included time-matched plasma-CSF sample pairs to determine CSF penetrance. Among 14 subjects treated with doses of 10, 15, or 20 mg of lenalidomide, the 16-hour (trough) plasma concentration was 0-220 ng/mL, and the intraventricular CSF concentration was 0-16.68 ng/mL, with a mean CSF trough concentration of 4.9 ng/mL. The CSF/plasma ratio, calculated on time-matched pairs where the CSF lenalidomide concentration was >0, was 0-49%. Further, this group found that there is a dose-dependent increase in CSF concentration with lenalidomide, with higher CSF/plasma partition coefficients at the 15 or 20 mg lenalidomide dose.[30]

For ibrutinib CNS penetrance, in a phase 1b trial ([NCT02315326](#)) by Grommes et al., 15 subjects with recurrent/refractory CNS lymphoma including PCNSL and SCNSL were given ibrutinib at doses from 560-840 mg orally daily and had CSF samples drawn at 2 hours post the cycle 2, day 28 dose. Mean CSF ibrutinib concentration was 3.105 ng/mL (equivalent to 7.05 nM; range, 0.305-9.22). In subjects receiving 560 mg of ibrutinib, the mean CSF concentration was 1.553 ng/mL (range 0.991-2.62). The mean CSF levels in subjects receiving 840 mg of ibrutinib was 3.992 ng/mL (range 0.305-9.22).[31] In our TEDDI-R study (NCT03964090) for PCNSL, subjects were treated at ibrutinib dose levels of 560 mg (6), 700 mg (4), and 840 mg (8). In these 18 subjects, the time to max concentration in the CSF was approximately 2 hours and the  $T_{1/2}$  was 18.1 (4.1-31.2) hours. In the 560 mg, 700 mg, and 840 mg ibrutinib cohorts, the median max CNS concentration was 1.4, 1.98, and 1.33 nM, respectively, and the median corrected area under the curve (AUC)  $AUC_{csf}/AUC_{plasma}$  was 43.4%, 35.1%, and 28.7%, respectively. These cohorts showed that there was not a proportional dose dependent increase in max CSF concentration or the areas under the curve at the 700 mg or 840 mg ibrutinib doses.[12] In relapsed/refractory CNSL, 2-hour-post mean CSF concentrations of ibrutinib monotherapy at doses of 560 to 840 mg daily was 0.77ng/ml (1.7nM) and 1.95ng/ml (4.4nM), respectively, and higher when checked at 2-hour-post at day 28 of therapy, 1.65ng/ml and 3.18ng/ml, respectively.[32]

In a case report of a patient with CLL with CNS involvement treated with venetoclax, time-matched plasma and CSF concentrations of venetoclax were obtained. The max and minimum concentrations at 2 hours and 23 hours post venetoclax were 1.2 and 0.52  $\mu$ g/mL in plasma, respectively, and 2.8 and 1.5 ng/mL in CSF, respectively. The plasma to CSF concentration ratio was 0.1%. [33] In unpublished data collected at the NCI on two subjects treated with off-label use of VIPOR for relapsed/refractory PCNSL using 800 mg venetoclax daily, the mean 2-hour post

dose CSF concentration was 2.35 ng/mL (2 samples) and the 24-hour post-dose CSF mean was 1.83 ng/mL (3 samples).

Given that most CNSL share biologic features with ABC DLBCL and that VIPOR demonstrates the most clinical activity in ABC DLBCL, a formal study including the VIPOR platform for CNSL is highly rational.

### 1.2.8 Safety Summary of VIPOR-based therapy in B-cell lymphoma

This study will utilize a novel combination of targeted agents and two important safety aspects will apply as part of the primary objective. First, the safety of VIPOR in patients with lymphoma involving the CNS. The safety of the combination has been established in over 58 patients with relapsed aggressive and indolent B-cell lymphomas without CNS involvement who were treated on an ongoing study at the NCI [NCT03223610]. The preliminary results have been presented at the 2020 Annual Meeting of the American Society of Hematology [34]. In these patients, most toxicity was hematologic and 16% and 7% of cycles were associated with G3 or G4 thrombocytopenia, respectively. Further, 15% and 7% of cycles were associated with G3 or G4 neutropenia which resulted in an amendment to ensure that all patients receive growth factor support. The most common G3/G4 non-hematologic toxicities were hypokalemia (17%), increased LFTs (9%), diarrhea (7%), and atrial fibrillation (5%). Other serious but rare toxicities that occurred included intracranial hemorrhage (N=1), tumor lysis syndrome (N=1), and pneumoperitoneum (N=1). Dose reductions were required on only 7% of cycles. We hypothesize that the toxicity of VIPOR will not be different in the participants included on this study.

## 2 ELIGIBILITY ASSESSMENT AND ENROLLMENT

### 2.1 ELIGIBILITY CRITERIA

#### 2.1.1 Inclusion Criteria

2.1.1.1 Participants must have histologically or cytologically confirmed primary diffuse large B-cell lymphoma of the CNS (PCNSL) or non-GCB diffuse large B-cell lymphoma with secondary involvement of the CNS (SCNSL). **NOTE:** Participants with B-cell lymphomas that were previously indolent but now involve the CNS (i.e., transformed

from previous follicular lymphoma, chronic lymphocytic leukemia, marginal zone lymphoma, and mantle cell lymphoma) **are eligible**.

2.1.1.2 Participants must have a disease that is relapsed or refractory after initial systemic treatment or be considered ineligible for standard frontline therapy with high-dose methotrexate due to one of the following criteria:

- Age  $\geq$  70 years
- Estimated glomerular filtration rate  $< 60 \text{ ml/min}/1.73\text{m}^2$
- Presence of ascites or pleural effusion

2.1.1.3 Participants must have evaluable disease by clinical exam (i.e., palpable lymphadenopathy, measurable skin lesions, etc.) and/or imaging (measurable lymph nodes or masses on CT or MRI and/or evaluable FDG-avid lesions on PET).

2.1.1.4 Participants with second malignancies not requiring active systemic therapy or premalignant conditions such as monoclonal B-cell lymphocytosis (MBL) or monoclonal gammopathy of undetermined significance (MGUS) are eligible.

2.1.1.5 Participants that are positive for hepatitis B core antibody (HBcAb), hepatitis B surface antigen (HBsAg), or hepatitis C antibody must have a negative hepatitis B and/or C viral load by polymerase chain reaction (PCR). See Section [4.1.2](#).

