#### 2.2.2.2 Laboratory Evaluations

- CBC with differential
- Chemistry panels including: Acute Care Panel (Sodium (NA), Potassium (K), Chloride (CL) Total CO2 (Bicarbonate), Creatinine, Glucose, Urea nitrogen, eGFR); Mineral Panel (Albumin, Calcium, Magnesium, Phosphorus); Hepatic Panel (Alkaline Phosphatase, ALT/GPT, AST/GOT, Total Bilirubin, Direct Bilirubin); and, 24-hour urine creatinine clearance (if needed to measure CrCl in cases where serum creatinine >1.5 mg/dl)
- Coagulation panel, including PT and aPTT
- HIV 1 /2 antibody, Hepatitis B surface antigen (HBsAg), Hepatitis B surface antibody (HBsAb), Hepatitis B core antibody (HBcAb), and Hepatitis C antibody (HCV Ab)
  - Participants who are HBsAg negative and HBcAb positive or HBsAg positive will have viral load testing by HBV PCR.
  - Participants who are HCV Ab positive will have viral load testing by HCV PCR.
- Urine and/or serum HCG in IOCBP (within 14 days prior to initiation of study treatment)
  - A pregnancy test (urine or serum) with a sensitivity of 25 mIU/mL must be done in accordance with Celgene Revlimid REMS™ guidelines for individuals of childbearing potential (IOCBP) only.

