#### 4.1.2 Prophylaxis of Hepatitis B reactivation

Participants who are positive for either Hepatitis B core antibody (HBcAb) or Hepatitis B surface antigen (HBsAg) and not acutely infected are at varying risk for reactivation of Hepatitis B especially when combined with novel agents like ibrutinib and rituximab. Participants may be included in the study provided that they have HBV DNA levels below the World Health Organization's cutoff of 100 IU/mL prior to starting therapy. These participants will be treated with entecavir (or equivalent) to prevent hepatitis B reactivation and should have HBV DNA levels obtained monthly during treatment, and at: End of Treatment, 30 Day Post-Treatment Safety Visit; and every 3 months for 12 months after the last cycle of therapy by means of real-time PCR with the use of an assay that has a sensitivity of at least 10 IU/mL.

If the HBV DNA assay becomes positive during combination therapy, study treatment should be held, and the participant should be immediately referred to a gastroenterologist or hepatologist for management recommendations.

If a participant's HBV DNA level exceeds 100 IU/mL while the participant is receiving antiviral medication, study treatment must be permanently discontinued

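### Hepatitis B entry is a negative PCR in Section 2.1.1.5 but HBV DNA below 100 IU/mL in Section 4.1.2, so detectable virus below 100 IU/mL is excluded by one rule and admitted by the other

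*Combined protocol and SAP*

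**What the plan says.** **Entry, Section 2.1.1.5.** Participants positive for hepatitis B core antibody, hepatitis B surface antigen or hepatitis C antibody "must have a negative hepatitis B and/or C viral load by polymerase chain reaction (PCR"). No IU/mL value is given, and the criterion refers the reader to Section 4.1.2.

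**Entry, Section 4.1.2.** The paragraph covers "Participants who are positive for either Hepatitis B core antibody (HBcAb) or Hepatitis B surface antigen (HBsAg) and not acutely infected". They may be included "provided that they have HBV DNA levels below the World Health Organization's cutoff of 100 IU/mL prior to starting therapy". They then receive antiviral prophylaxis, with HBV DNA measured monthly during treatment and at set visits afterwards, "with the use of an assay that has a sensitivity of at least 10 IU/mL".

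**Hold, Section 4.1.2.** "If the HBV DNA assay becomes positive during combination therapy, study treatment should be held", with referral to a specialist. No level is attached to positive.

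**Discontinuation, Section 4.1.2, repeated in Section 3.8.1.** "If a participant's HBV DNA level exceeds 100 IU/mL while the participant is receiving antiviral medication, study treatment must be permanently discontinued".

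**Screening, Section 2.2.2.2.** "Participants who are HBsAg negative and HBcAb positive or HBsAg positive will have viral load testing by HBV PCR". No cutoff and no assay sensitivity are stated. Section 3.4.2 confirms that the viral load serves both eligibility and monitoring for reactivation, again without a cutoff.

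**The concern.** Two sections set an entry condition for the same hepatitis B population, and the conditions differ. One is qualitative (a negative PCR) and the other quantitative (below 100 IU/mL). They give different answers for anyone whose virus is detectable but below 100 IU/mL, and the cross-reference from the first section to the second does not say which governs.

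The criterion has a safety purpose: Section 4.1.2 itself describes these participants as at varying risk of reactivation. The conflict therefore decides who with detectable virus is exposed to the regimen, and whether enrolling such a person is an eligibility deviation. The undefined word positive carries the same uncertainty into the hold rule during treatment.

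**Working it through.** No sample-size figure depends on this point, so the check applies each rule to the same HBV DNA values.

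**Inputs.** The entry rules come from Sections 2.1.1.5 and 4.1.2. The hold and discontinuation rules come from Section 4.1.2. The 100 IU/mL cutoff is stated there for entry and for discontinuation. The 10 IU/mL sensitivity is stated there for monitoring only. Using 10 IU/mL as the detection limit at screening is an assumption of this check.

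| HBV DNA (IU/mL) | Eligible, 2.1.1.5 | Eligible, 4.1.2 | Positive assay if seen on therapy | Discontinue if seen on antiviral (above 100) |
|---|---|---|---|---|
| undetected, or 5 | yes | yes | no | no |
| 10 | no | yes | yes | no |
| 50 | no | yes | yes | no |
| 99 | no | yes | yes | no |
| 100 | no | no | yes | no |
| 101 | no | no | yes | yes |

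The two entry rules disagree only for detectable virus below 100 IU/mL. At 100 IU/mL and above both exclude. A more sensitive screening assay would move the lower edge below 10 IU/mL, and a less sensitive one would move it up.

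**Can negative simply mean below 100 IU/mL?** If so, positive would mean 100 IU/mL or more. The rule to hold on a positive assay would then nearly coincide with the separate rule to discontinue above 100 IU/mL on antiviral medication. A hold step ahead of a discontinuation step has content only if positive includes detectable levels below 100 IU/mL. On that reading, Section 4.1.2 admits participants at levels that would count as a positive assay on treatment.

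**Hepatitis C.** Section 4.1.2 gives no competing threshold for hepatitis C, so the requirement in Section 2.1.1.5 stands alone and there is no conflict.

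**Design figures.** With 10 participants and success declared at 7 or more:
- At a true rate of 50%: (120 + 45 + 10 + 1)/1024 = 176/1024 = 0.1719, matching the stated 17.2%.
- At a true rate of 80%: the binomial probability of 7 or more is 0.8791, matching the stated 87.9%.

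Neither figure uses the hepatitis B rules, so both are unaffected.

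**The case against.** The best defence is that Section 2.1.1.5 is the controlling criterion and that Section 4.1.2, which sits among the concomitant-medication rules, only adds a necessary condition that any PCR-negative participant meets anyway. This is a possible reading, but the protocol does not state that order of precedence. It also leaves the 100 IU/mL entry figure with no work to do wherever the assay detects lower levels. The opposite reading, that the cross-reference defines negative as below 100 IU/mL, runs into the near-coincidence of the hold and discontinuation rules. Two defensible readings with opposite results for the same person still need a correction.

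Four stronger conclusions are tempting, and the documents do not support them.

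- *The band is 10 to 99 IU/mL as a matter of record.* The 10 IU/mL sensitivity belongs to on-treatment and follow-up testing. The screening PCR has no stated sensitivity, and Section 2.1.1.8 allows eligibility laboratory tests to be done outside the NIH.
- *Anyone with detectable virus is caught in the conflict.* At 100 IU/mL or more both entry rules exclude.
- *A participant admitted with detectable virus meets the hold rule at once.* The rule refers to the assay becoming positive during therapy. Testing is monthly and these participants are on prophylaxis. A hold would need virus still detectable at the first on-treatment test, and a reading in which someone already positive can become positive.
- *One such participant costs 10 percentage points of the primary endpoint (1 of 10).* Section 10.4.2 counts completion of at least 2 cycles without stopping for toxicity. A hold is not a stop, Section 3.3.1 permits delays of up to 6 weeks, and the hepatitis B discontinuation rule applies above 100 IU/mL, outside the disputed band. Nothing says that a hepatitis B hold counts as failure.

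**Conclusion.** The contradiction stands and is wrong as written. For participants positive for hepatitis B core antibody or surface antigen, detectable HBV DNA below 100 IU/mL is excluded by Section 2.1.1.5 and admitted by Section 4.1.2. Nothing elsewhere in the protocol resolves it, because negative and positive are never given a value. A linked gap is that the hold rule does not say whether a participant admitted with detectable virus meets it at the first on-treatment test.

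The size is small. The documents do not say how many participants would fall in the band, and in a trial needing 10 evaluable participants it may be none. The lower edge of about 10 IU/mL rests on the assumption that the screening assay matches the monitoring assay. The point deserves correction because the criterion governs who is exposed to a reactivation risk that the protocol itself names.

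**What to change.** Reconcile Sections 2.1.1.5 and 4.1.2 so that one HBV DNA entry rule applies. Define negative and positive, and use those definitions consistently in the entry, hold and discontinuation rules. State the sensitivity required of the screening PCR, and say how the hold rule applies to anyone admitted with detectable virus, if the reconciled rule allows that. The choice of limit belongs to the clinical team, and this review does not favour one.

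The cost is a wording amendment to the eligibility criterion and Section 4.1.2, with matching wording in Section 2.2.2.2. Sample size, the 7-of-10 rule and the analysis do not change.
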